Therefore, we hypothesize that APRV could be safely used in patients with severe TBI as it does not increase their ICP and compromising their Cerebral Perfusion Pressure (CPP), while preventing hypoxemia and hypercapnia in these patients.

Project Primary Goal

This pilot study, to the best of our knowledge, is the first study that specifically investigates the efficacy of APRV among patients with severe TBI. We aim to investigate whether APRV can safely oxygenate patients without compromising their ICP and CPP.

Study Personnel

Principal Investigator: [name]

Co-investigator: [name] (point of contact)

Drs. [name], [name], [name], [name], [name], [name], [name], [name], [name].

Study Methodology

Methods:

We will conduct an observational crossover study. We aim to recruit 50 patients with severe TBI requiring intracranial pressure monitoring during their stay at the Neuro Trauma ICU at the R Adams Cowley Shock Trauma Center. Each patient at admission will initially receive a primary mode of mechanical ventilation as determined by the attending trauma intensivists.

12-18 hours after recruitment, continuous monitoring of patients' ICP and hemodynamic status (ICP, HR, RR, SpO₂, EtCO₂, MAP, CPP, SpO₂, and EtCO₂) will commence to collect patients' baseline data for 30 minutes. Patients will then undergo low tidal volume mechanical ventilation (LOTV), serving as a control mode of ventilation, for 2 hours prior to switching back to the primary mode of ventilation for 30 minutes. Next, patients will be placed on APRV for 2 hours. While receiving APRV, patients' ICP and hemodynamic status will be continuously monitored and recorded for comparison and analysis. After 2 hours of APRV, patients will be switched back to their previous mode of ventilation and more data are collected for another 30 minutes. This sequence of ventilation is illustrated in figure 1.

Intracranial pressure will be measured every 15 minutes during the study period. While undergoing low tidal volume ventilation and APRV, patient's volume statuses and cardiac functions will also be assessed using a non-invasive, non-radioactive modality such as Transthoracic Echocardiography.

Figure 1. Sequence of mechanical ventilation and data collection.

[figure not shown]

Figure 2. Flow chart of APRV Protocol:

[figure not shown]
[figure not shown]

Figure 3. Flow Chart for LOTV protocol

Inclusion Criteria

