- Intracranial pressure monitoring
- Mechanically ventilated

Exclusion Criteria

- Age < 18
- Pregnant women
- Prisoners
- Initial mode of ventilation = APRV
- Providers' judgments

Consent:

The patients will not be able to consent for themselves, due the severity of their conditions. We will seek consent from legally authorized representative if available or patients' next-of-kin.

Outcomes

- Primary outcome: ICP
- Secondary outcomes: MAP, CPP, SpO₂, EtCO₂, any interventions for ICP or for hemodynamic instability.

Analysis Plan

Data Security:

Patient's data will be recorded on a standardized Microsoft Excel spreadsheet. This spreadsheet will first be password-protected, then encrypted by commercial 128-bit encryption software (www.boxcryptor.com). The encrypted spreadsheet then will be stored in a secure, password-protected online storage with extra security designed for corporation (OneDrive for Business by Microsoft Corporation, Redmond WA; <https://onedrive.live.com/about/en-nz/business/>).

These measures of security allow maximal collaborations between investigators while enhancing safety for patients' protected health information.

Data Analysis:

We aim to report our findings as following:

Table 1. Patient Demographics
Number of patients
Age (years)
Gender
BMI
Mechanism of injury Motor vehicle collision, n (%) Gunshot wound, n (%) Fall, n (%)
GCS score
ISS
Primary mode of mechanical ventilation
PaO ₂ /FiO ₂ ratio
ICU length of stay (days)
Hospital length of stay (days)
Mortality

Table 2. Outcome Measurements						
Dependent Measure (Mean, Interquartile)	Baseline	LOTV	APRV	Conventional MV		p-value
				Pre-APRV	Post-APRV	
ICP						
MAP						
CPP						
CVP						
Heart Rate						
Respiratory Rate						
SpO _p						
EtCO ₂						
Volume status by TTE						
Therapeutic interventions for ICP, blood pressure						

Table 3. Adverse Events	
Patients not tolerating APRV N, (%)	

Causes N, (%)	Elevated ICP
	CPP < 50
	Hypoxemia
	Hypercapnia
	Tachycardia

All continuous variables will be reported as mean with interquartile values (IQR).

Estimated Study Length

There were 1259 patients with isolated blunt TBI (Abbreviated Injury Scale of brain was ≥ 2 while AIS for other body region was ≤ 2) admitted to the R Adams Cowley Shock Trauma Center in 2013. Therefore, we estimate that we will be able to recruit 2-3 patients per week.

Our pilot study is expected to finish recruitment within 6-8 months.

Target Conferences

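### Intolerance and its causes are counted for APRV only: the adverse-event table has no control count for LOTV, and no table counts the listed event types in either mode

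*Combined protocol and SAP*

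**What the plan says.** The Methods section describes a crossover in 50 patients. Each receives LOTV for 2 hours, "serving as a control mode of ventilation", then 30 minutes back on the primary mode. "Next, patients will be placed on APRV for 2 hours". The Project Primary Goal asks whether APRV oxygenates safely without compromising ICP and CPP, and the Hypothesis adds prevention of hypoxemia and hypercapnia.

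The Data Analysis section plans three tables.

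- **Table 1** holds demographics, length of stay and mortality.
- **Table 2** has a column for each mode and a p-value. Its row heading is "Dependent Measure (Mean, Interquartile", and the text below the tables repeats the rule: "All continuous variables will be reported as mean with interquartile values (IQR". It also has one event-type row, "Therapeutic interventions for ICP, blood pressure", which corresponds to the secondary outcome "any interventions for ICP or for hemodynamic instability".
- **Table 3**, on adverse events, has one headline count, "Patients not tolerating APRV N" with its percentage, and N (%) for five causes of that intolerance. It has no LOTV row or column.

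**The concern.** An APRV-only intolerance count is a sensible feasibility measure for a pilot. The stated aim, however, is safety, and the design supplies a control for judging it. Patients with severe TBI may have high ICP, low CPP, desaturation or tachycardia on any ventilator mode. Followed as written, the adverse-event table gives a percentage for APRV and nothing to set beside it. A reader could not tell whether the patients who failed APRV had also failed LOTV a few hours earlier.

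A second gap applies to both modes. Table 3 counts causes of intolerance. On a plain reading, a patient with a brief untreated excursion who stays on APRV is not in it, and the same patient on LOTV appears in no table either. Counts could be extracted later from the monitoring data, but most of the definitions would then be chosen after the data had been seen.

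**Working it through.** The documents give no event rate, SD, margin or named test, so there is no planned figure to reproduce. The first step is a check of the table shells. The others are illustrations whose counts and readings are all assumed.

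**1. What each table counts for the five Table 3 items**

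| Quantity | APRV | LOTV |
|---|---|---|
| Patients not tolerating the mode, by cause | Table 3, 5 of 5 causes | none, 0 of 5 |
| Patients with the event, tolerated or not | none | none |
| Treated ICP or blood-pressure problems | Table 2 | Table 2 |
| Mean and quartiles of ICP, CPP, SpO2, EtCO2, heart rate | Table 2 | Table 2 |

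The asymmetry is in the first row. The second row is empty for both modes.

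**2. What a control count adds.** Take N = 50 from the Methods. Assume that 5 patients do not tolerate APRV, that all 50 enter both windows, and that the same definition is used in both. Alone, 5/50 = 10%, with an exact (Clopper-Pearson) 95% CI of 3.3% to 21.8%. With an LOTV column, the paired difference is (APRV-only - LOTV-only)/50, here with the Tango score interval.

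| On LOTV | APRV-only / LOTV-only | Difference, points (95% CI) | Exact McNemar p |
|---|---|---|---|
| nobody | 5 / 0 | +10 (2.2 to 21.4) | 0.063 |
| 2 other patients | 5 / 2 | +6 (-5.3 to 18.2) | 0.45 |
| 5 other patients | 5 / 5 | 0 (-13.5 to 13.5) | 1.00 |
| the same 5 patients | 0 / 0 | 0 (-7.1 to 7.1) | 1.00 |

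In the last line there are no discordant pairs, and the limits are ±z²/(N + z²) = 3.84/53.84 = 7.1%. Table 3 as planned reads 5/50 in all four cases.

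**3. What Table 2 can miss.** "Intracranial pressure will be measured every 15 minutes during the study period", so a 2-hour window has 120/15 = 8 intervals and 8 or 9 readings. Assume a steady ICP of 12, with one reading of 30 in 5 of 50 patients.

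- Patient mean with 9 readings: (8×12 + 30)/9 = 14.0.
- Group mean: (5×14 + 45×12)/50 = 12.2, with both quartiles at 12.
- For this shift, a simulated paired t-test (20,000 runs) gives p < 0.05 in 18.6% of runs if the SD of paired differences is 1, and in 5.9% if it is 4. Chance alone gives 5%.

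If the same five sat steadily at 14 on LOTV, both columns would show 12.2 (12, 12), with 0 against 5 patients having a reading of 30. This example is deliberately extreme. It shows that the summaries do not determine the counts, and this holds for both modes.

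**4. What Table 2 would show.** Assume a sustained CPP of 45 against 75 in the remaining patients.

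- 5 patients: (45×75 + 5×45)/50 = 72.0.
- 12 patients: (38×75 + 12×45)/50 = 67.8.

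Shifts of this kind would be visible in Table 2, although not as a number of patients.

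**The case against.** The strongest case on the other side has four parts.

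- **Table 3 measures feasibility of a new mode in a pilot, not event incidence.** This stands. A reader might infer that the plan counts hypoxemia, ICP crossings and the rest on APRV while leaving them uncounted on LOTV. The table does not support that, because it lists causes of not tolerating APRV. Brief untreated events are counted in neither mode. The direct mirror of Table 3 is an LOTV intolerance count.
- **Table 2 already compares the modes on the variables behind all five causes, and on interventions.** This largely stands for sustained or treated ICP and blood-pressure problems. It would be wrong to say that the plan ignores safety on LOTV. Table 2 still gives no number of patients to set beside Table 3.
- **The order is fixed, so a control count cannot attribute events to APRV.** This also stands. It limits what the comparison means, but it does not make an uncompared percentage more informative.
- **The flow charts in Figures 2 and 3 may contain tolerance criteria for LOTV.** They were not available for this review and may do so. Criteria in a flow chart are still not a planned count, and all three table shells are in the text.

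**Conclusion.** The point holds as a gap in planned reporting. Intolerance and its causes are counted for APRV only, with no matching count for the declared control, and no table counts patients with the five event types in either mode. No figure in the documents is wrong, and the primary outcome, ICP, is still compared between modes in Table 2.

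The size depends on counts that the documents do not give. Under the assumptions above, the same 5/50 on APRV fits anything from a 10-point excess to none. Those values assume one event definition in both modes, all 50 patients entering both windows, and each APRV event leading to intolerance. A reader might go further and infer that serious sustained harm would be hidden, or that an LOTV column would establish cause. The documents support neither inference: Table 2 would show sustained shifts, and LOTV always precedes APRV. This is a cheap change worth making before analysis, not a flaw that undermines the study.

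**What to change.** 1. Keep the APRV intolerance count and its causes unchanged, labelled as a feasibility measure. Add an LOTV column to Table 3 for patients not tolerating LOTV, with the same five causes.
2. As separate rows, count patients with each of the five listed event types during each 2-hour window. Use one definition per event, written before analysis, identical for both modes and consistent with any criteria in Figures 2 and 3. Apply it to the monitoring data at the same reading interval in both windows.
3. Give the number entering and completing each window, and a descriptive paired difference with 95% CI among patients who entered both. State that LOTV always comes first, so period and carry-over effects cannot be separated from the mode effect.

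**Cost.** The event counts appear to need no new measurement, since Table 2 already requires LOTV values for ICP, CPP, SpO2, EtCO2 and heart rate. The LOTV intolerance count also needs a record of who did not tolerate LOTV and why. Only CPP below 50 has a threshold in the visible text, so up to four definitions must be written unless the figures contain them. Intervals will be wide at N = 50, and windows stopped early will have shorter exposure. At small counts the score interval and the exact test can disagree: for 5 against 0 the interval excludes zero while p = 0.063. The comparison should therefore stay descriptive.

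### Table 3 counts only intolerance of APRV, with no matching count for LOTV, no per-patient event count for the 30 minutes after APRV, and no row for barotrauma, neurological worsening, bradycardia or other serious events

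*Combined protocol and SAP*

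**What the plan says.** The Hypothesis section states: "we hypothesize that APRV could be safely used in patients with severe TBI as it does not increase their ICP". The Project Primary Goal reads: "We aim to investigate whether APRV can safely oxygenate patients without compromising their ICP and CPP". The planned sample is 50 patients, and the work is called a pilot.

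Under Methods, each patient has a 30-minute baseline, 2 hours of LOTV as control, 30 minutes back on the primary mode, 2 hours of APRV, and then a return to the previous mode, where "more data are collected for another 30 minutes".

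The planned output is three tables under Data Analysis:

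- **Table 3 (Adverse Events)** has one count, "Patients not tolerating APRV N" (with percent). It is split by cause: elevated ICP, CPP below 50, hypoxemia, hypercapnia and tachycardia. Only CPP has a threshold in the table, and no event window is stated.
- **Table 2 (Outcome Measurements)** has columns for Baseline, LOTV, APRV, Pre-APRV and Post-APRV. Its rows include ICP, MAP, CPP, heart rate, SpO₂ and EtCO₂, plus "Therapeutic interventions for ICP, blood pressure". The summary rule is "All continuous variables will be reported as mean with interquartile values (IQR").
- **Table 1 (Patient Demographics)** lists GCS once and mortality once, neither tied to a study period.

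The secondary outcomes also include "any interventions for ICP or for hemodynamic instability".

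**The concern.** The study means to say something about safety, and Table 3 is where a reader will look for it. Three things limit what that table can support.

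First, it has no comparator. LOTV is the control mode, yet patients who have an elevated ICP or a low CPP on LOTV are not counted in the same way. In severe TBI such events can occur on any mode, so an APRV count alone cannot separate an effect of the mode from the background rate.

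Second, intolerance is not the same as harm. A patient may have an event and still complete the 2 hours, and an event may follow the switch back. Table 3 does not ask for either to be counted.

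Third, the list of causes is closed. The Introduction names raised intrathoracic and airway pressure as risks of ventilation, and high airway pressure as the worry with APRV. Yet no planned table reports airway pressure or pressure injury. Neurological worsening and bradycardia are not events anywhere in the text shown, and there is no open category.

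**Working it through.** The plan gives no event rate, power calculation or safety margin, so there is no stated figure to reproduce. The check is mainly a comparison of what each table would hold.

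**Step 1. Where would each kind of event appear?**

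| Event | Table 3 | Elsewhere |
|---|---|---|
| One of the five causes, leading to intolerance of APRV | counted | Table 2 summaries |
| The same event on LOTV | no count | Table 2, LOTV column (summary) |
| ICP or blood-pressure episode after APRV, treated | no count stated | Table 2 interventions row, Post-APRV column |
| ICP or blood-pressure episode after APRV, untreated | no count stated | Table 2 summaries only |
| Desaturation after APRV | no count stated | Table 2 SpO₂ summary only |
| Bradycardia | no row | Table 2 heart rate summary only |
| Pneumothorax or other barotrauma | no row | none in the text shown |
| Neurological worsening | no row | none (GCS is listed once, in Table 1) |
| Death | no row | Table 1, not tied to a period |

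**Step 2. How well does a period summary show one episode?** Inputs: n = 50 (Methods). The ICP values are assumptions: 12 mmHg without an episode and 40 mmHg during one, an excess of 40 − 12 = 28 mmHg. The change in the group mean with k affected patients is k × 28 / 50.

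- k = 1: 28 / 50 = 0.56 mmHg
- k = 2: 56 / 50 = 1.12 mmHg
- k = 3: 84 / 50 = 1.68 mmHg

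Raising one patient's value moves each quartile by at most one place in the ordering. It moves neither quartile if that patient was already above the upper one.

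If the high value lasts for one reading only, the shift is smaller. ICP is taken every 15 minutes. Counting 120 / 15 = 8 readings on APRV and 30 / 15 = 2 after it, and assuming that readings are averaged within patient (the plan does not say):

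- one reading on APRV: 28 / 8 = 3.5 mmHg in that patient's mean, and 3.5 / 50 = 0.07 mmHg in the group mean;
- one reading after APRV: 28 / 2 = 14 mmHg in that patient's mean, and 14 / 50 = 0.28 mmHg in the group mean.

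**Step 3. Are the two windows comparable in length?** LOTV plus the pre-APRV period is 2 + 0.5 = 2.5 hours. APRV plus the post-APRV period is also 2 + 0.5 = 2.5 hours. A like-for-like count is therefore available within the existing sequence.

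**Step 4. What could a complete count show with 50 patients?** For zero events, the upper limit is 1 − α^(1/50):

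- one-sided 95%: 1 − 0.05^(1/50) = 5.8%
- upper limit of a two-sided 95% interval: 1 − 0.025^(1/50) = 7.1%

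The chance of at least one event is 1 − (1 − p)^50. For assumed true rates of 1%, 2%, 5% and 10% it is 39.5%, 63.6%, 92.3% and 99.5%. Rare harms could be missed even if every one were listed. This is context for reading a zero, not a measure of the gap in Table 3.

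**The case against.** The strongest reply is that the stated question is narrow. It concerns ICP, CPP and gas exchange, and four of the five causes in Table 3 (elevated ICP, low CPP, hypoxemia, hypercapnia) match it directly. In a pilot, the absence of a wider harm list does not contradict the plan's own aim. That stands, and it keeps this point at the level of a reporting improvement. It does not supply the missing LOTV count, which the narrow question needs as well.

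A reader might infer that harm in the 30 minutes after APRV is never counted. The documents do not support that. Table 2 carries a Post-APRV column that includes therapeutic interventions, and interventions are a secondary outcome, so a treated ICP surge on switching back would be recorded. What is missing is a per-patient count of the events themselves. The Table 2 row is also limited to ICP and blood pressure, whereas the secondary outcome speaks of hemodynamic instability.

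A reader might also infer that a patient with a pneumothorax or pupil change after APRV must be reported as free of adverse events. That goes too far. Table 3 states no event window, and the APRV and LOTV flow charts, which may define intolerance, are not shown, so nothing can be drawn from their absence. Equally, heart rate is monitored and reported for every period, so bradycardia is not invisible, and a death would appear in Table 1. The narrower statement holds: the text shown provides no event row for these harms.

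**Conclusion.** The point holds as a gap in the safety reporting. Table 3 gives one count, for one of the two modes compared, with five causes and no open category. Effects after APRV reach the reader through period summaries and an interventions row, and death through a demographic table. A statement that APRV was used safely would then rest on an intolerance count with no control beside it, supported by means and quartiles that can absorb a single severe episode.

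Its numerical size cannot be derived from the documents. The 0.56 mmHg shift rests on assumed ICP values, and the 5.8% and 7.1% limits only describe what 50 patients can exclude. The conclusion assumes that the missing flow charts do not themselves prescribe a matched event count; definitions of intolerance in those charts would sharpen Table 3 but would not add rows or a comparator to it. It is a modest change worth making before the data are tabulated.

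**What to change.** In Table 3, report the number and percent of patients with each listed event, whether or not the mode was stopped, in two columns:

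- from the switch to APRV to the end of the post-APRV period;
- from the start of LOTV to the end of the pre-APRV period.

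Apply the same written event definitions to both columns. Take them from the flow charts if they are given there; otherwise the investigators should state them. Keep the intolerance count as a separate line.

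Add rows for pneumothorax or other barotrauma, charted neurological worsening, bradycardia or other arrhythmia, arrest or death during the sequence, and an open row for any other serious event. Because these patients are sedated, the neurological row should say which charted signs count.

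No new procedure or patients are needed. The cost is some extra chart abstraction, assuming that these events are charted routinely, and a possibly less favourable event count. One limit remains: LOTV always comes first, so the two columns are a descriptive comparison and differences may partly reflect time.

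### Table 2 plans window means, IQRs and one unlabelled p-value, so it will not show the precision of the within-patient APRV minus LOTV change in ICP

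*Combined protocol and SAP*

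**What the plan says.** The Methods describe a single fixed sequence in which each patient receives "low tidal volume mechanical ventilation (LOTV), serving as a control mode of ventilation" for 2 hours, returns to the primary mode for 30 minutes, and then receives APRV for 2 hours. The hypothesis is that "APRV could be safely used in patients with severe TBI as it does not increase their ICP". ICP is the primary outcome. On sampling, the Methods say "Intracranial pressure will be measured every 15 minutes during the study period", and that ICP and haemodynamic values during APRV "will be continuously monitored and recorded for comparison and analysis". The target is 50 patients.

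The Data Analysis section consists of three table shells and one reporting rule: "All continuous variables will be reported as mean with interquartile values (IQR)". Table 2 is headed "Dependent Measure (Mean, Interquartile)" and has five window columns (Baseline, LOTV, APRV, Pre-APRV and Post-APRV) and a single p-value column. Table 3 has a row for "Patients not tolerating APRV N" (with percentage) and lists elevated ICP among the causes.

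The readable text names no test, contrast, paired difference, standard error, confidence interval, alpha or margin. The three figures are not shown, but their captions concern the ventilation sequence and the two ventilation protocols, not the analysis.

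**The concern.** The design pairs each patient's APRV window with the same patient's LOTV window, but the planned tables describe each window separately. With complete pairs, a reader can subtract the two means to obtain the mean change. The reader cannot obtain its precision, because the IQRs describe spread between patients within a window, whereas the precision of the change depends on how strongly the two windows correlate within patients.

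The p-value does not fill the gap. Five windows allow 5 × 4 / 2 = 10 pairwise contrasts, or one overall test, and the column does not say which is meant. Without a named contrast and test, no standard error can be worked back from it.

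This matters more than usual because the hypothesis is the absence of a rise. A non-significant p-value would not support that claim; the reader needs the largest mean rise that the data still allow.

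There is a second route to a misleading result. If some patients have no usable APRV window, the difference of the two column means is no longer the paired change. If patients who stop APRV because ICP rose are left out, the change is biased downward, towards the hypothesis.

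**Working it through.** **Inputs.** From the protocol: n = 50, with LOTV and APRV in every patient. The sample size of 50 cannot be reproduced, because no SD, effect size, alpha, power or precision target is given. Everything else below is assumed for illustration: equal IQRs in both windows (8 mmHg, with 6 and 12 as a range), roughly normal values so that SD = IQR / 1.349, a mean difference of 1.5 mmHg, and within-patient correlation ρ from 0 to 0.9.

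**Formulas.**
- SD of the paired difference: SD_d = SD × √(2(1 − ρ))
- 95% CI half-width: t(0.975, 49 df) × SD_d / √50 = 2.0096 × SD_d / 7.071 = 0.284 × SD_d
- Paired t = 1.5 / (SD_d / √50), on 49 df
- Unpaired t = 1.5 / (SD × √(2/50)), on 98 df

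The factor 0.284 needs only n = 50 complete pairs. SD_d is the number that the planned tables omit.

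**IQR 8 mmHg.** SD = 8 / 1.349 = 5.93.

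| ρ | SD_d | Half-width | 95% CI for the change (mmHg) | Paired t | Paired p |
|---|---|---|---|---|---|
| 0 | 8.39 | 2.38 | -0.88 to 3.88 | 1.26 | 0.21 |
| 0.5 | 5.93 | 1.69 | -0.19 to 3.19 | 1.79 | 0.080 |
| 0.7 | 4.59 | 1.31 | 0.19 to 2.81 | 2.31 | 0.025 |
| 0.9 | 2.65 | 0.75 | 0.75 to 2.25 | 4.00 | 0.0002 |

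All four rows produce the same LOTV and APRV means and IQRs in Table 2. The unpaired test gives t = 1.5 / (5.93 × 0.2) = 1.26, p = 0.21, whatever ρ is. A printed p of 0.21 would therefore fit a clear rise (unpaired test, ρ = 0.9) and also data too imprecise to tell (paired test, ρ near 0).

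**Other IQRs.** For ρ from 0 to 0.9, the half-width runs from 1.8 to 0.6 mmHg at IQR 6 (SD 4.45), from 2.4 to 0.75 at IQR 8, and from 3.6 to 1.1 at IQR 12 (SD 8.90). The ratio is always √(1 / 0.1) = 3.2, so the conclusion does not depend on the IQR chosen.

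**Leaving out patients who do not tolerate APRV.** Suppose the mean change over all 50 is 1.5 mmHg and k patients with a given mean rise are dropped. The rest show (50 × 1.5 − k × rise) / (50 − k).

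| Assumed mean rise in those left out (mmHg) | k | Mean change in the rest (mmHg) |
|---|---|---|
| 6 | 2 | 63 / 48 = 1.31 |
| 6 | 5 | 45 / 45 = 1.00 |
| 6 | 10 | 15 / 40 = 0.38 |
| 10 | 5 | 25 / 45 = 0.56 |

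**The case against.** **This is a pilot with outline tables.** A shell without a CI column does not forbid one, and nothing says that a non-significant p-value will be read as no increase. That is true, so the point concerns what the plan commits to. As written, it commits to summaries that cannot answer its hypothesis, and precision is a main product of a pilot.

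**The contrast is inferred.** The protocol never names APRV minus LOTV, and the Pre-APRV and Post-APRV windows lie closer in time to APRV. This is fair, but LOTV is the only mode called the control, and the lack of a named contrast is part of the defect.

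**The illustration is stretched.** An unpaired test would be odd in a crossover, one p-value for five windows may mean an overall repeated-measures test, and ρ = 0 is extreme for windows about half an hour apart. Part of this stands: over ρ from 0.5 to 0.9, the half-width varies about 2.2-fold (1.69 to 0.75) rather than 3.2-fold. An overall test, however, would say even less about APRV against LOTV.

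**The exclusion bias is speculative.** The text does not say that such patients are left out, the unseen APRV flow chart may say what happens to them, and the counts and rises are invented. This stands as a limit: the bias is conditional and its size is unknown. Still, Table 2 has no count of pairs and the text has no rule for these patients.

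**A confidence limit does not settle causation.** In a fixed LOTV-then-APRV order, time is confounded with mode, and interventions for ICP (a listed secondary outcome) could mask a rise. This stands; the interval covers sampling error only.

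**Conclusion.** The concern holds. The planned tables give the mean in each window but not the precision of the within-patient change, and the single p-value cannot stand in for it while its contrast and test are unnamed. For n = 50 complete pairs, the 95% CI half-width is 0.284 times an SD of differences that the plan does not report. Under the assumed IQR of 8 mmHg, the largest mean rise still allowed could be anywhere from 2.25 to 3.88 mmHg with identical Table 2 entries.

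The mmHg figures rest on assumed IQRs, normality and correlations; the dependence on an unreported correlation does not. The downward bias from leaving out patients who do not tolerate APRV is a conditional risk, not an established feature of the plan. The collected data are not harmed, so the defect can be fully repaired before analysis.

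**What to change.** 1. Fix one summary value per patient per window, for example the mean of the 15-minute readings.
2. Add to Table 2 the mean within-patient APRV minus LOTV difference with its SD, number of pairs and 95% CI, for ICP, MAP, CPP, SpO₂ and EtCO₂. State that the p-value tests this paired contrast.
3. Base the statement about no increase on the upper limit of the ICP interval, reported as the largest mean rise the data still allow, and put the fixed-order limitation beside it. A yes/no verdict would need a margin set by the team before analysis; the documents give none and none is proposed here.
4. Include patients who do not tolerate APRV by using the readings recorded on APRV before it was stopped, and report how many APRV windows are shortened or missing.
5. If APRV minus Pre-APRV is also wanted, label it secondary, since LOTV is the stated control.

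The cost is one extra column and one footnote, from data already being collected. Two limits remain: a shortened APRV window rests on fewer readings, so its summary is noisier and may understate the rise, and no table change removes the effect of the fixed order.

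### Every continuous variable, including the primary outcome ICP, is to be summarised as a mean with quartiles, which gives no SD and no precision for the within-patient comparison

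*Combined protocol and SAP*

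**What the plan says.** The Data Analysis section gives one summary rule and no exceptions: "All continuous variables will be reported as mean with interquartile values (IQR". The header of Table 2 carries the same format, "Dependent Measure (Mean, Interquartile", over columns for baseline, LOTV, APRV and the two conventional-ventilation periods, with one p-value column.

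The Outcomes section names "Primary outcome: ICP" and "Secondary outcomes: MAP, CPP, SpO₂, EtCO₂, any interventions for ICP or for hemodynamic instability". All of these appear in Table 2, with CVP, heart rate, respiratory rate and volume status by echocardiography. The last two rows, volume status and therapeutic interventions, sit under the same header, although nothing says they are continuous.

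Table 1 includes "ICU length of stay (days" and "Hospital length of stay (days" beside mortality, and also age, BMI, GCS, ISS and PaO2/FiO2. No SD, standard error, median or confidence interval is mentioned anywhere, and there is no rule for skewed variables. The planned size is in Methods: "We aim to recruit 50 patients with severe TBI requiring intracranial pressure monitoring".

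**The concern.** The mean and the quartiles answer different questions. Quartiles are rank-based and describe spread about a median. The spread that goes with a mean is the SD. A reader given a mean with quartiles cannot form a standard error without assuming a shape for the data, and is not told the median that would reveal skew.

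The design makes this matter more. Each patient receives LOTV and then APRV, so the quantity of interest is the change within a patient. Column-by-column means give the average change (when the same patients fill both columns) but say nothing about its spread or precision.

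Two further consequences follow from applying one format to every row. In a strongly skewed or ceiling-limited row, the printed mean may fall outside the printed quartiles. In the interventions row, which is a named secondary outcome, the format does not show how many patients needed treatment.

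**Working it through.** The plan gives no SD, effect size or data, so there is no figure of its own to reproduce. The inputs are the summary rule, the Table 2 header and n = 50. Every distribution below is an assumption.

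**1. Recovering an SD from quartiles.** For normal data IQR = 2 × 0.6745 × SD = 1.349 SD, so SD = IQR/1.349. For log-normal data with median 1 and log-SD s:

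- mean = exp(s²/2)
- quartiles = exp(±0.6745 s)
- SD = mean × √(exp(s²) − 1)

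At s = 0.5: IQR = 1.401 − 0.714 = 0.687, and 0.687/1.349 = 0.510. The true SD is 1.133 × 0.533 = 0.604. The ratio is 0.84.

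At s = 1.0: IQR = 1.963 − 0.509 = 1.454, and 1.454/1.349 = 1.078. The true SD is 1.649 × 1.311 = 2.161. The ratio is 0.50.

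The back-calculated SD is therefore too small under right skew. Since sample size scales with the SD squared, anyone planning from it would use 0.84² = 71% or 0.50² = 25% of the number needed.

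**2. Mean against its own quartiles.** The log-normal mean exceeds the upper quartile when s²/2 > 0.6745 s, that is s > 1.349 (a coefficient of variation of about 2.27). Simulating 40,000 samples of n = 50 gives the chance that the sample mean lies outside its interquartile range:

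| s | Mean / median | Upper quartile / median | Chance outside |
|---|---|---|---|
| 0.5 | 1.13 | 1.40 | 0.04% |
| 0.8 | 1.38 | 1.72 | 2.7% |
| 1.0 | 1.65 | 1.96 | 11% |
| 1.2 | 2.05 | 2.25 | 27% |
| 1.5 | 3.08 | 2.75 | 55% |

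At s = 1.0 the mean is still inside the quartiles in the population, but Φ(s/2) = Φ(0.5) = 69% of patients lie below it.

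**3. A ceiling.** Suppose SpO2 is 100% in 40 patients, 98% in 5, 92% in 3 and 85% in 2. The mean is (4000 + 490 + 276 + 170)/50 = 98.72 and both quartiles are 100, so the mean lies below the lower quartile.

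**4. Interventions.** If fewer than 25% of patients have any intervention, both quartiles are 0. Ten of 50 patients with one intervention each give a mean of 10/50 = 0.2 with quartiles 0 and 0. One patient with ten interventions gives the same entry. The mean times 50 returns the total, 10, but not the number of patients treated.

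**5. The within-patient change.** If both periods have the same SD and correlation r, the SD of the change is SD × √(2(1 − r)). This is 1.00 SD at r = 0.5, 0.77 SD at r = 0.7 and 0.45 SD at r = 0.9. The same per-period summaries are compatible with all three, so neither quartiles nor a per-period SD supplies the SD of the change. It has to be reported directly.

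**The case against.** The strongest reply is that this is presentation only. The rule changes no estimate, test, sample size or data item, and the patient-level data are kept in a spreadsheet from which an SD or median can be computed at any time. That stands, and it limits the weight of the point.

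The sentence may also be a slip of mean for median. That is plausible but cannot be shown. The pairing occurs twice, and a slip would still need correcting. Even corrected to a median, the rule would give no SD and nothing on the paired change.

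Three stronger readings are tempting, and the documents do not support them.

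- A reader might infer that the mean will fall outside its quartiles for the main outcomes. Nothing in the documents suggests such skew for ICP, CPP or MAP. The log-normal case fits length of stay best, and that is a descriptive Table 1 row, not an outcome. With mild skew (s up to 0.5) it almost never happens.
- A reader might infer that safety events would be hidden. The mean still returns the event total, and Table 3 reports patients not tolerating APRV, with causes, as N (%). What is lost is the number of patients treated in each period. Table 3 does not fill that gap, because it counts intolerance of APRV and has no LOTV entry. The summary sentence itself covers only continuous variables, so interventions are caught through the table header alone.
- A reader might infer that the study fails a stated aim of planning a later trial. The protocol calls itself a pilot, but its stated goal concerns safe oxygenation without harm to ICP or CPP, and it mentions no later trial. The use of an SD for planning is a reasonable expectation of a pilot, not a commitment in the text.

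Treating GCS and ISS as continuous under this rule is likewise a reading, since the plan does not classify them.

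**Conclusion.** The point holds as a reporting flaw of minor to moderate weight. Followed exactly, the plan gives a mismatched summary of the primary outcome, no SD, and no spread or confidence interval for the APRV minus LOTV change. These conclusions come from the text alone and need no distributional assumption.

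The size of the secondary effects does depend on assumptions. A mean outside its interquartile range requires strong skew or a ceiling. The 84% and 50% recovery of the SD, and the chances from 0.04% to 55%, are log-normal illustrations, and the SpO2 row is a constructed example. None of this biases an estimate, invalidates a comparison or alters the target of 50 patients.

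**What to change.** Replace the single sentence in Data Analysis with a rule by type of variable, and change the Table 2 header to match:

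- **ICP, CPP, MAP, CVP, heart rate, respiratory rate, EtCO2, SpO2, PaO2/FiO2, age and BMI:** both mean (SD) and median (IQR). Giving both avoids a choice made after seeing the data.
- **GCS, ISS, ICU and hospital length of stay:** median (IQR).
- **Therapeutic interventions:** n (%) of patients in each period, with the total count. The LOTV and APRV periods last 2 hours and the others 30 minutes, so only the first two compare directly.
- **Volume status by echocardiography:** n (%) if it is scored in categories, otherwise as for the other continuous rows. The plan should say which.
- **Within-patient change:** the mean APRV minus LOTV difference in ICP and in CPP, with its SD and 95% CI. The plan should also say how repeated readings (ICP is taken every 15 minutes) become one value per patient and period.

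No new data are needed. The cost is one rewritten paragraph, one header and slightly larger tables. Correcting the pairing alone would not supply the SD of the change, so the last item is needed in its own right.
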